	Email [contact]			
	[contact]			

STUDY SUMMARY

It may be useful to include a brief synopsis of the trial for quick reference. Complete information and, if required, add additional rows.

Study Title	Boosting Baby Communication and Play: Optimising Video Feedback for Perinatal Mental Health			
Internal ref. no. (or short title)	BOOST-2: Boosting Baby Communication and Play			
Study Design	Case series			
Participants	The study will include women who:			
	 Are using community perinatal mental health services Are a primary caregiver of a child aged 2 to 3 months 			
	3) Are capable of giving ir	formed consent		
	4) Are aged 16 to 65			
Planned Sample Size	N = 10	N = 10		
Treatment duration	3 to 5 months	3 to 5 months		
Follow up duration	5 months	5 months		
Planned Study Period	01/07/2021 to 31/03/2021			
	Objectives	Outcome Measures		
Primary	To evaluate the feasibility and acceptability of the adapted Video feedback intervention for Positive Parenting (VIPP), for mothers using perinatal mental health services and their 2 to 6 month old infants	1) % of trained clinicians implementing at least 1 VIPP intervention case 2) % of mothers invited to participate who give informed consent to do so 3) % of mothers initiating and completing the VIPP intervention 4) mother and clinician ratings of the therapeutic alliance during VIPP 5) participants' own accounts of their experiences of the feasibility and acceptability of the intervention, assessed using qualitative interviews		

BOOST-2 Boosting Baby Communication & Play

Secondary	To establish pre-post effect	1) Parental Stress Scale
	sizes and confidence	2) Parent Expectations
	intervals on outcomes	Survey
	relating to parenting stress,	3) Mother Object Relations
	parental self-efficacy, the	Scale – Short Form
	parent-child bond, parent-	(MORS-SF)
	child interaction and	4) Parent-Infant Interaction
	emotional dysregulation	Observation Screen
		5) Difficulties in Emotion
		Regulation Scale

FUNDING AND SUPPORT IN KIND

FUNDER(S) (Names and contact details of ALL organisations providing funding and/or support in kind for this trial)	FINANCIAL AND NON FINANCIALSUPPORT GIVEN
Barts Charity: [name]	£42,637.34
Central and North West London NHS Foundation Trust: [name]	£ 9,998.00

ROLE OF STUDY SPONSOR AND FUNDER

The sponsor is City University of London. The sponsor is responsible for ensuring that the study design meets appropriate standards, that it has the required resources for initiation and management and that all applicable regulatory approvals have been received before the study starts. The sponsor is also responsible for ensuring that arrangements are in place for appropriate conduct and reporting while the study is active and that there is a clear dissemination and data retention plan once the study has closed. Should the study fail to comply with the applicable laws and regulations, or demonstrate that it is failing to achieve reasonable milestones and this is unlikely to be rectified, the sponsor has the right to withdraw sponsorship.

The funders are The Barts Charity and Central and North West London NHS Foundation Trust. They will have no role in conducting or making decisions about study design, conduct, data analysis and interpretation, manuscript writing, or dissemination of results.

Protocol contributors

The protocol was written by the Chief Investigator [name]. The protocol was reviewed by a representative of the sponsor to ensure that it complied with Health Research Authority guidance.

KEY WORDS:

Perinatal mental health
Infant mental health
Parent-infant intervention

LIST of CONTENTS

GENERAL INFORMATION	Page No.
TITLE PAGE	
RESEARCH REFERENCE NUMBERS	
SIGNATURE PAGE	
TRIAL SUMMARY	
FUNDING	
KEY TRIAL CONTACTS	
ROLE OF SPONSOR AND FUNDER	
ROLES & RESPONSIBILITIES OF TRIAL MANAGEMENT COMMITTEES, GROUPS AND INDIVIDUALS	
LIST of CONTENTS	
LIST OF ABBREVIATIONS	
TRIAL FLOW CHART	
SECTION	

1 BACKGROUND

Between 10 and 20% of women develop a mental illness during pregnancy or within the first year after having a baby. Perinatal mental illness carries a total long-term cost to UK society of £8.1 billion for each one-year birth cohort (Bauer et al. 2014). Nearly three-quarters of this cost relates to adverse long-term impacts on the child rather than the mother, including mental health and behaviour problems. Negative impacts on child development are in part likely to stem from early difficulties in parent-infant interactions and relationships, that have been linked to maternal perinatal mental illness. In particular, mothers experiencing perinatal illness have been shown to find it harder to understand and respond sensitively to their infant's communication. Such difficulties have been linked in meta-analytic studies to early parent-child relationship problems and subsequent problems in children's socioemotional development (DeWolff & van lizendoorn 1997, Ranson & Urichichuk 2008). Birth to age three is a unique period of neuroplasticity, with neurogenesis in brain regions responsible for cognitive and emotional development beginning to rise rapidly at 6 months and peaking at 36 months, driven by early life experiences (Shonkoff & Phillips 2000, Siegel 2015). Intervening at this stage offers a critical opportunity to prevent the lifelong damaging effects of early problematic socioemotional experiences (Shonkoff & Phillips 2000). In line with this, the NHS Long-Term plan has identified increasing access to evidencebased care for women with moderate to severe perinatal mental health difficulties, including parent-infant interventions, and increasing support for children's mental health from birth onwards, as a priority (NHS 2019). Perinatal mental health services, which treat women with moderate to severe difficulties, are ideally placed to offer such interventions. However, the evidence base for implementing parent-infant interventions in NHS services is minimal. There are currently to our knowledge no published trials of such interventions in perinatal mental health services. Video feedback parent-infant interventions specifically target the types of problems with parentchild interaction that are believed to partially explain the link between perinatal mental illness and poor child outcomes i.e. mothers' ability to understand and respond sensitively to their infants' communication. Meta-analysis has shown that the most effective interventions for improving parental sensitivity incorporate direct feedback to the parent based on recording and playing back videos of parent-infant interaction (Bakermans-Kranenburg et al. 2003). Our team of applicants has recently successfully tested one such intervention – the video feedback for positive parenting intervention (VIPP)- in three perinatal mental health services in London (The BOOST trial, ISRCTN 10052006). Trials in other at-risk groups - mothers with bulimia nervosa, insecure attachment or low sensitivity, and infants with behavioural problems - have shown that VIPP is more effective than control treatments in improving parental sensitivity, reducing child behaviour problems, and improving child socio-emotional development (Kalinauskiene et al. 2009, Klein Velderman et al. 2006, Stein et al. 2006, Van Zeijl et al. 2006). Our team has recently completed the NIHR-funded BOOST trial: the first randomised controlled trial of this intervention in perinatal mental health services. This was a small feasibility trial in 34 women using perinatal mental health services. Uptake of the intervention was high, with 95% of women randomised to VIPP initiating the intervention and 75% completing all 6 sessions. Feedback from mothers receiving the intervention and from perinatal mental health clinicians showed that VIPP was received very positively. Mothers consistently told us that VIPP helped to give them a different perspective on their relationship with their child,

boosting their confidence in their parenting abilities, and giving them new insights into how to understand and respond positively to their children's communication. This effect was reflected in the quantitative data on changes in parental sensitivity in the intervention and control groups, as shown in Figure 1 in the attachment. Ratings of parental sensitivity were conducted based on analysis of video data by a psychologist who was blind to intervention allocation, with clear positive intervention effects. In the group who received VIPP, just 35% were rated as sensitive in their interactions with their children at baseline; this rose to 50% at the 5-month follow-up (postintervention) and 64% at the 8-month follow-up. By contrast, in the control condition mothers who did not receive VIPP, average levels of sensitivity dropped over time. Whilst 50% of control mothers were rated as sensitive in their interactions with their children at baseline, this dropped to 44.5% at the 5-month follow-up and 33.25% at the 8-month follow-up.

2 RATIONALE

Despite these promising findings, the BOOST trial also highlighted two challenges for VIPP intervention delivery with mothers using perinatal mental health services. The aim of the proposed research is to test a modified protocol for intervention delivery, in order to address these two challenges. This is an essential pre-requisite before the intervention can be tested in a future largescale randomised controlled trial.

Challenge One. Minimum child age for intervention delivery. VIPP was originally developed for children aged 6 months and above. However, women most commonly come into contact with perinatal mental health services during pregnancy or soon after giving birth. During the BOOST trial, we found that by the time their child was aged 6 months, women had often been discharged from the service, either due to improving sufficiently in their mental health so as to no longer require support from the service, or due to having disengaged from contact with the service. This meant that some women and their children who could have benefited from the intervention were not able to receive it. The standard intervention protocol contains elements that may not be suitable for very young babies, such as filming parents building towers of blocks with their babies. Therefore, to increase the feasibility of VIPP delivery in perinatal mental health services, and to optimise recruitment to a future randomised controlled trial, we have adapted the intervention protocol to include activities that are appropriate for younger babies. These adaptations were based on a survey of 50 mothers with young babies.

Challenge Two. Evidence from interviews with clinicians and mothers experiencing mental health difficulties (Dunn et al. 2020) suggest a need to modify the intervention to target maternal emotional dysregulation during parent-infant interaction, as this is a major contributor to parent-infant relationship problems in this population (Bartsch et al. 2015, Murphy 2016, Yelland et al. 2015), and is not currently addressed by VIPP. Parental emotional dysregulation predicts parent-infant relationship problems, poor parental sensitivity, child behaviour problems and adolescent emotional dysregulation, mediated by parents' difficulty in acknowledging and regulating their child's emotions (Brake et al. 2020, Buckholdt et al. 2014, Carreras et al. 2019, Dittrich et al. 2019, Han & Shaffer 2013, Stepp et al. 2012, Yelland et al. 2015). Relatedly, parents in our feasibility trial told us that VIPP was most helpful when they received feedback on challenging and mutually emotionally dysregulating parent-infant interaction. Therefore, to optimise the potential for the intervention to improve emotional dysregulation during parent-infant interaction, we have modified it to include brief psychoeducation materials on helpful emotion regulation strategies. These were drawn from grey literature on parenting and evidence-based approaches including dialectical behaviour therapy and mentalization based therapy and evaluated for potential helpfulness and feasibility in a survey of 50 mothers with young babies.

We now need to pilot the modified intervention with Mums using perinatal mental health services, to check it is feasible for clinicians to deliver, and to gain Mums' and clinicians' feedback. Using a case series of 10 women, we will evaluate 1) feasibility of intervention delivery by perinatal mental health staff; 2) acceptability of the intervention for mothers using perinatal mental health services; 3) pre-post changes in parental sensitivity, parenting stress, parental self-efficacy, the parent-child bond and emotional dysregulation. Our findings will inform a future planned largescale randomised controlled trial of the intervention in this population.

2.1 Assessment and management of risk

- 1) Risk of participant distress. Participants may feel criticised or judged by being asked to take part in parent-focussed research, or whilst receiving feedback during the video feedback sessions. We will manage this by training both researchers and clinicians to emphasise throughout that this is a positively-focussed, non-judgemental intervention aiming to boost parents' confidence and highlight their strengths. We will train the therapists delivering to debrief at the end of each session to help parents process their feelings around watching and discussing the videos, and to incorporate ideas from dialectical behaviour therapy (an evidence-based treatment for personality disorder (Stoffers et al. 2012) to help parents manage their self-judgements during the intervention. Participants will be interviewed by researchers in a sensitive, empathic and non-judgemental style. Researchers will emphasise to the participants that they do not have to answer any questions if they do not want to. These techniques were reported to be very helpful, in feedback interviews with mothers taking part in our previous BOOST research project.
- 2) Risk of criminal or other disclosure. Participant responses and data will be kept confidential within the research team and stored pseudo-anonymously. However, participants will be informed that if they disclose information which indicates an immediate and serious risk of severe self-harm or harm to others, or if there are concerns for the neglect or abuse of children, their confidentiality will be broken and their clinical team informed.
- 3) Risk to participant or researcher.
 - a. Coronavirus pandemic. As a default, all participant research assessments, and delivery of the VIPP intervention, will take place virtually over video conferencing software. If preferred by the participant and/or necessary for technical reasons, home visits may take place if allowed by the participant's NHS Trust, agreed to by the participant and researcher, and City University of London individualised coronavirus risk assessments are satisfactory (e.g. neither researcher nor participant have recent coronavirus symptoms nor a condition requiring shielding). Any home visits occurring will following social distancing recommendations (e.g. 2m distance between participants and researcher), all parties aged above 10 years old will wear masks and the researcher will use anti-viral hand gel on entering and leaving the premises.

 b. Lone working. Once allowed by the participating NHS Trusts, if agreed to by the participant
 - and if City University of London risk assessment thresholds for the researcher and participant are not exceeded, researchers may visit participants in their homes to conduct assessments. To minimise risk to researchers, City University of London policy on lone working will be adhered to, whereby prior to the first visit with an unknown participant, the researcher will complete a risk assessment, and during the visit itself and any subsequent visits will continue to remain aware that risk within a home visit situation can escalate and will therefore continue

to dynamically assess risk throughout the visit. Additionally, a buddy system will be implemented whereby before each visit, the researcher will notify a colleague of the address that they are visiting and the expected end-time of the visit. The researcher will then contact the buddy colleague once they have left the premises of the participant's home. If more than 30 minutes elapse after the expected end time of the visit, with no contact from the researcher, the buddy will call the researcher. A code word will be established to enable the researcher to notify the buddy if they are in trouble. The buddy will then notify the local or national police and ask them to undertake a welfare visit to the participant's home address. If the buddy cannot reach the researcher on the phone after 3 attempts, the buddy will then notify the local or national police and ask them to undertake a welfare visit to the participant's home address.

3 STUDY DESIGN

Case series of N = 10 mothers using perinatal mental health services and offered our adapted version of VIPP. Case series are useful for establishing the feasibility of a novel or adapted intervention (Kooistra et al. 2009, Stewart et al. 2019). They are often used for piloting and gaining feedback on adapted versions of intervention protocols before moving to conducting a full randomised controlled trial. For instance in our previous study we piloted an adapted version of VIPP for parents experiencing personality-related mental health difficulties in 9 mothers, before moving to test it in a trial; and the ACORN study piloted an adapted version of the Towards Parenthood intervention in a small case series of pregnant women before moving to test it in a trial (ISRCTN10052006; Wilkinson et al. 2016). We will follow guidance on designing high quality case series by using a prospective design; clearly defining our population, intervention, outcomes, and follow-up; and not making causal inferences about the treatment effect (Kooistra et al. 2009). Our planned sample size of 10 follows established good practice in carrying out case series in previous related research (ISRCTN10052006; Wilkinson et al. 2016) and in the wider literature, where case series usually have 10 or fewer participants with the average being 8 (Abu-Zidan et al. 2012). Additional mothers will be recruited should initial recruits discontinue the intervention prematurely or be lost to follow-up.

3.1 Intervention

Six 90 minute Baby Communication and Play sessions using the Video-feedback Intervention to promote Positive Parenting (VIPP), to be delivered every two weeks. VIPP is a manualised intervention which provides parenting feedback based on videoed interactions between parent and child. VIPP helps parents to recognise, understand and respond sensitively to their child's behaviour. Positive and non-judgemental feedback is used to focus on parents' strengths and help them feel confident in their parenting. As in our previous BOOST research study, based on feedback from our expert-by-experience co-investigator [name], and our PPI group of parents with a diagnosis of a personality disorder, we have incorporated additional elements into the training for clinicians delivering the intervention, to help them focus on building trust and addressing parents' concerns around feeling judged. For this new project, as detailed above, we have adapted the intervention protocol to include activities that are appropriate for younger babies, and to include brief psychoeducation materials on helpful emotion regulation strategies. We have gained management support for perinatal mental-health clinicians to train in and deliver the intervention. Sessions will primarily be delivered using Zoom video conferencing software with participants situated in their homes and clinicians situated in their clinic. The therapists will receive supervision on every session by certified VIPP supervisors.

BOOST-2 Boosting Baby Communication & Play

Participants receiving the intervention will also access treatment as usual from perinatal, adult mental health and/or social services during the trial.

4 STUDY SETTING

This is a multi-centre study. The study will be run in perinatal mental health services, in Central and North West London NHS Foundation Trust, Oxleas NHS Foundation Trust and East London NHS Foundation Trust. All participants will be recruited from and treated in perinatal mental health services. Each site will be both a recruitment site and an intervention site.

Requirements for a site:

- 1) Community perinatal mental health service
- 2) Management agreement for clinicians to train in and deliver the video feedback for positive parenting intervention

Requirement for individuals delivering the intervention:

- 1) A registered or trainee mental health professional working in a perinatal mental health service
- 2) Attendance of intervention training provided by the research team
- 3) Commitment to deliver the intervention to at least 2 participants over the duration of the research

5 **ELIGIBILITY CRITERIA**

5.1 Inclusion criteria for service-user participants

The study will include women (people assigned female at birth and/or currently identifying as female) who:

- Are using community perinatal mental health services
- Are a primary caregiver of a child aged 2-3 months at intervention initiation
- Are capable of giving informed consent
- Are aged 16 to 65

5.2 **Exclusion criteria for service-user participants**

The study will exclude:

- Families where a sibling or co-parent is participating in the trial
- Families in which the eligible child has a clinical diagnosis of a learning difficulty, developmental disorder or sensory impairment.
- Families in which the eligible parent has English language or learning difficulties that are sufficiently severe to prevent them completing study measures even with assistance.

5.3 Inclusion criteria for clinician participants

The study will include clinicians who:

- Were trained in the video feedback for positive parenting intervention as part of this study OR
- Have management responsibility for a clinician who was trained in the video feedback for positive parenting intervention as part of this study

5.4 Exclusion criteria for clinician participants

The study will exclude clinicians who:

N/A

6 STUDY PROCEDURES

Intervention or Procedure	Total number of interventions or procedures received by each participant as part of research protocol	How many times would each participants receive each intervention or procedure as part of routine care	Average time taken per intervention or procedure	Who will conduct the intervention or procedure	Where will it take place
Clinician discusses research with potential participant	1	0	15 minutes	A clinician responsible for the participant's care in a perinatal mental health service	Video conferencing software or phone
Participant gives verbal consent for researcher contact	1	0	5 minutes	A clinician responsible for the participant's care in a perinatal mental health service	Video conferencing software or phone
Researcher contacts potentially eligible participants to invite to take part in research assessment	1	0	10 minutes	Researcher	By phone, video, email or post
Written informed consent for	1	0	15 minutes	Researcher	Video conferencing software,

participation in full study					email or post (patient preference)
Self-report questionnaires	2	0	20 minutes	Researcher or self-administered	Video conferencing software, online, email or post
Video assessment of parent-child interaction	2	0	10 minutes	Researcher	Video conferencing software
Receive VIPP Baby Communication and Play Sessions	6	0	90 minutes	A registered or trainee mental health professional who has been trained by the research team to deliver Baby Communication and Play Sessions	Video conferencing software
Qualitative interview	1	0	30 minutes	Researcher	Video conferencing software or phone

6.1 Recruitment

Service-user participants will be recruited from perinatal mental health services. Clinicians will identify patients meeting inclusion criteria and ask if they will consent to researcher contact. Following this verbal consent to contact, researchers will contact eligible patients identified by clinicians, to give further information about the research project. Following this, if the patient is willing to participate, they will sign a consent form.

Clinician participants will be recruited from perinatal mental health services. Clinicians who were trained in the video feedback for positive parenting intervention as part of this study, or have management responsibility for a clinician who was trained in the video feedback for positive parenting

intervention as part of this study, will be asked to take part in a qualitative feedback interview at the end of the study.

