6.1.1 Participant identification

Service-user participants will be identified by a clinician responsible for their care in a perinatal community mental health service, who will refer them to the research based either on the clinician's clinical judgment that they meet eligibility criteria. The clinician will make a judgement on the inclusion and exclusion criteria. Clinicians will obtain verbal permission from mothers to pass their details to the research team and these will be emailed to the researchers over NHS-mail to NHS-mail encrypted server. This verbal consent will be recorded in the potential participant's medical records. The researchers will then confirm that the participant meets eligibility criteria.

Only a member of the patient's existing clinical care team will have access to patient records in order to identify eligible participants.

Clinician participants will be approached directly by the research team.

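### Mothers enter only if their own clinician raises the study; no rule requires every eligible mother to be approached and no log records those passed over, so completion, alliance and interview findings may come from mothers picked as likely to engage

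*Protocol*

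**What the plan says.** **Entry.** Protocol 6.1.1 states: "Service-user participants will be identified by a clinician responsible for their care in a perinatal community mental health service". The same clinician screens: "The clinician will make a judgement on the inclusion and exclusion criteria". Section 6.1 gives the step that follows: "Clinicians will identify patients meeting inclusion criteria and ask if they will consent to researcher contact". The procedures table in section 6 likewise starts with a clinician responsible for the mother's care discussing the research with her.

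**Checks.** Researchers come in after referral: "The researchers will then confirm that the participant meets eligibility criteria". They cannot look for other eligible mothers, because "Only a member of the patient's existing clinical care team will have access to patient records in order to identify eligible participants".

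**Delivery.** Section 4 has every site both recruit and treat. A therapist must be "A registered or trainee mental health professional working in a perinatal mental health service" and must make a "Commitment to deliver the intervention to at least 2 participants over the duration of the research". No sentence separates the therapist from the referring clinician.

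**Design claims.** Section 3 says "We will follow guidance on designing high quality case series by using a prospective design". It adds a clearly defined population, intervention, outcomes and follow-up, and no causal inference. How mothers are drawn from the defined population is not among the features listed.

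**Use.** Section 7.3 takes as feasibility indices the share of trained clinicians who deliver at least one case, the share of invited mothers who consent, the share who start and complete, and alliance ratings from mothers and clinicians. Interviews add to the judgement of acceptability.

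**The concern.** Selection at the point of approach acts before any index is counted. A clinician with a small number of cases to deliver has an understandable reason to begin with mothers she expects to attend, and the index on clinicians delivering at least one case adds to it. The protocol does not invite this, but nothing in it would prevent or expose it.

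At stake are completion, alliance and the interview findings, which are the study's primary evidence on feasibility and acceptability. Section 2 (Challenge One) gives a particular reason to care: in BOOST, some women had disengaged from the service before their child reached 6 months, and the adaptation is meant to reach women earlier. If mothers thought likely to disengage are not approached, the group that partly motivated the adaptation is under-sampled, and good completion would say little about it. Approaches that were never made and never logged cannot be reliably reconstructed afterwards.

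**Working it through.** **1. Is there a rule or record anywhere?** Set side by side:

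| Step | Who acts | Could it show or limit selection? |
|---|---|---|
| Identify and raise the study (6, 6.1, 6.1.1) | Clinician responsible for care | No order of approach and no log |
| Search records (6.1.1) | Care team only | Researchers cannot see mothers not referred |
| Confirm eligibility (6.1.1) | Researchers | Covers referred mothers only |
| Consent percentage (7.3) | Counted from mothers invited | Starts after the selection step |
| Analyse everyone recruited (7.4) | Analyst | Acts after recruitment |

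Every safeguard comes after the approach.

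**2. The plan's own accrual figure.** Section 7.2 plans 10 mothers from July to October 2021. Over four calendar months, 10 / 4 = 2.5 a month, which reproduces the stated 2 to 3.

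**3. Approaches needed.** Section 7.2 reports that 52% of mothers approached in BOOST were eligible and consented. 10 / 0.52 = 19.2, so about 20 approaches across three Trusts fill the study. Replacement under 7.1 raises this: if 10 completers were sought at BOOST's 75% completion (section 1), 10 / 0.75 = 13.3 recruits and 13.3 / 0.52 = 25.6 approaches. The number of eligible mothers is not given, so the room for choice is unknown.

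**4. Illustration on assumed figures.** Take 75% as the true completion rate among all eligible mothers. Assume likely engagers complete at 90% and others at 50%. Their share w solves 0.9w + 0.5(1 − w) = 0.75, so w = 0.625. If engagers are k times as likely to be approached, their share among those approached is wk / (wk + 1 − w), assuming equal consent in both groups:

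- k = 2: 1.25 / 1.625 = 0.769; completion 0.5 + 0.4 × 0.769 = 0.808
- k = 4: 2.5 / 2.875 = 0.870; completion 0.848
- only engagers approached: completion 0.90

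**5. A second set of assumptions.** Half of eligible mothers are likely completers and half are not, averaging 75%, but 80% of those referred are likely completers. P(at least 9 of 10 complete) = 10p⁹(1 − p) + p¹⁰, which is 0.24 at p = 0.75.

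| Assumed rates | Expected completion | P(at least 9 of 10) |
|---|---|---|
| 0.85 / 0.65 | 81% | 0.41 |
| 0.90 / 0.60 | 84% | 0.51 |
| 0.95 / 0.55 | 87% | 0.62 |

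**6. Scale against chance.** The sampling standard error of completion at 75% with n = 10 is √(0.75 × 0.25 / 10) = 0.137. The shifts in step 4, about 6 to 15 points (0.6 to 1.5 mothers of 10), are mostly within one standard error.

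**The case against.** The case against has weight.

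- **The stated rule is eligibility.** Nothing tells clinicians to select on expected engagement, and the motive is inferred. This stands, and it is why the point is worded as what may happen.
- **Better than BOOST.** A reader might infer that selection would make the adapted protocol look as good as or better than BOOST. The documents do not support that. Section 7.2 says BOOST mothers were also approached by their clinician, so BOOST may carry similar selection. Section 7.3 compares pre-post effects with BOOST and sets no completion comparison.
- **A bias of 6 to 15 points.** This range follows from the assumed rates and approach ratios in the working, none of which has a source in the protocol. It shows what is plausible and is not an estimate.
- **Larger pre-post change.** A reader might extend the point to the pre-post effects. The direction is not supported: likely engagers could begin with better sensitivity and have less room to improve.
- **A surplus of mothers to choose from.** The eligible pool is not given, and the window of 2 to 3 months at intervention initiation (5.1) is narrow.
- **Breach of the guidance cited in section 3.** That cannot be checked from the protocol.
- **Small pilot, no causal claims.** True, but disclaiming causal inference does not make completion and alliance representative of the mothers the service sees.
- **Burden and capacity.** Approaching everyone regardless of therapist availability would be impractical. This is fair, and the fix allows for it.

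**Conclusion.** The point holds as a weakness in the recruitment procedure, not as an error or contradiction. Entry depends on the treating clinician's choice to raise the study, unapproached eligible mothers leave no trace, and referrer and therapist may be the same person. Completion, alliance and interview findings may therefore reflect mothers thought likely to engage, and the planned indices cannot show whether they do.

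The size of any bias cannot be found from the documents. The illustrations, 81% to 90% observed against an assumed true 75%, rest on assumed completion rates and assumed selection. The conclusion does not depend on those figures. It rests on the absence of a rule and a record at the one step where selection occurs, and on that record being lost if it is not kept at the time. The change should be made because it is cheap and cannot be made retrospectively; the study is not invalid without it.

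**What to change.** - **6.1 and 6.1.1:** state that, while a therapist slot is open, each service approaches every woman meeting 5.1 and 5.2, in the order her child enters the age window, until recruitment is complete, including any replacements under 7.1. State that expected engagement is not a reason to withhold an approach; accepting it would preserve the selection.
- **Log:** the care team keeps an anonymous list of eligible mothers approached and not approached, with a reason for each non-approach (for example clinical risk, no therapist slot, missed). For each recruit it records whether the referrer was also the therapist. Researchers need no access to records.
- **Section 3:** add consecutive approach to the design features.
- **7.3:** report these counts and reasons beside the feasibility percentages.

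**Cost:** protocol wording, a little care-team time for screening and logging, and the loss of clinicians' free choice of first cases. No extra participants or visits are needed. If consecutive approach proves unworkable at a site, the log alone still makes the selection visible.
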